Specific Aim 3: Explore dose and sub-population effects of THR and BA interventions by comparing effect size differences in THR and BA groups to a (1) 10-week wait-list control group (n = 20); (2) Hybrid intervention group (n = 20) (five weeks BA followed by five weeks THR); and (3) most severely impaired subsample (n = 20) of the THR study population randomized following psychiatric hospitalization. *H3a. The BA group will show significantly greater improvements on Aim 1 outcomes compared to those randomized to the waitlist control group. H3b. The Hybrid group will show a similar response pattern as the THR group.*

Specific Aim 4: Explore anecdotal observations of the study intervention personnel (i.e. instructors and volunteers) by providing study intervention personnel with a written survey of questions to gather information about their study observations and experiences. *H4. The written reflections of study personnel about their interaction with the study population will provide anecdotal support for the study findings.*

Our preliminary data demonstrate that physiological data collection is feasible with ASD youth engaged in THR at the proposed PATH international ¹⁷premiere accredited riding centers: (1) northern Colorado where access to psychiatric care is limited and (2) Portland, ME near a specialized ASD psychiatric hospital program. We also partially replicated our previous results, demonstrating cortisol is a viable target mediator of THR effects on aberrant behaviors in ASD youth.¹⁸ Our team has collaborated across the two study sites for over five years and has the necessary clinical and technical experience to conduct this next phase of THR research.

Background and Significance:

ASD population with co-occurring psychiatric disorders

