Randomization: For the Colorado site, the study statistician will generate random group assignment numbers stratified according to Leiter-II¹⁰⁶ nonverbal IQ standard score (>85 NVIQ and ≤ 85 NVIQ) to assign treatment (THR) or control groups (BA or waitlist/hybrid). After at least 24 participants have completed the waitlist/hybrid arm, this assignment will discontinue. Those assigned to the waitlist group will, after completing their 10-week waiting period and post assessments, participate in the Hybrid group (5 weeks BA and 5 weeks THR). For the Maine site, the study statistician will generate random group assignment numbers as specified above to assign to the treatment (THR) or control group (BA).

Riding center site screening (Visit II): THR and BA participants will complete a 45-minute -individual screening at their study site's riding center with a THR instructor. In the event that a THR or BA participant could not complete this riding center for behavioral reasons (e.g., feeling overwhelmed by the novel environment), participants will be allowed no more than two attempts for this screening. This will involve interviewing caregivers about participants' needs and abilities, caregivers completing the ABC-C Irritability screener, as well as engaging participants in a review of riding center safety rules, and practice with physiological equipment (i.e., putting saliva sampling rod in mouth and wearing the Shimmer3 EDA and ECG monitors) . **For THR participants:** Sit at an art table and engage in an art or puzzle activity about horses, enter the arena, engage in a 10-minute mounted activity on the horse, and then dismount. **For BA participants:** Sit at art table and engage in an art or puzzle activity about horses. Participants will then be assigned to a THR or BA group appropriate to their age and abilities. THR participants will be matched with a horse based on their unique needs consistent with standard practices of the THR industry.¹⁷ Participants may be excluded from the study at this time due to exclusion criteria discussed earlier. The waitlist/Hybrid participants recruited for the Colorado site will follow both a combined version of BA and THR screening routine similar to the screening protocol previously described .

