General consideration of statistical analysis: Prior to the start of any formal analyses, data for each variable will be examined to identify unusual values that need to be queried, including outliers, patterns of missing values, and non-Gaussian distributions (i.e., have significant skewness and kurtosis). Baseline demographic and clinical characteristics will be summarized using descriptive statistics and grouped by intervention arms. Between-arm difference in demography and baseline variables will be examined using t-test or chi square test respectively for continuous and categorical variables. Any imbalance that could potentially be a confounding factor for the outcome will be adjusted for in statistical models (see below). The primary efficacy analysis will use the “intent-to-treat (ITT)” principle to test our study hypotheses under practical and realistic conditions where not all participants follow or complete the program. All randomized participants will be analyzed in the ITT analyses. Linear Mixed Effect Model (LMM) will serve as the primary method to handle missing values. Other analyses such as completer analysis and analyses with imputed data will be deemed as sensitivity analysis for efficacy examination. However, for mediation analysis, only participants with both the

mediator (intervening) variable and outcome variables available will be included to explore mechanism of the intervention effect. No interim analysis will be conducted. In all analyses, a $p \leq 0.05$ will be considered significant. SAS and Mplus software will be used for these analyses.

AIM1: Efficacy assessment (for H1a-1c): LMM with unstructured covariance will be used to model baseline and end of treatment (EoT or T_2) primary and secondary outcome measures as well as expanded outcomes where fixed effects include evaluation time (baseline or EoT) and intervention arm indicator (THR/BA), as well as their interaction.

[figure not shown]
Estimate of the interaction will be used to quantify effect size and tested for statistical significance.

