hybrid intervention (H3b), data during the hybrid treatment period will be compared to within-person outcome data during the wait period. Moreover, we will compare hybrid treatment participants to all BA and THR participants. For both hypotheses 3a and b, LMM models similar to the one for Aim 1 efficacy analysis will be used. Again, the between-group difference in outcome change between baseline and 10 weeks will be used to assess efficacy and tested for statistical significance. The 95% confidence interval for efficacy and corresponding effect size (Cohen's D) will be reported. Any imbalanced confounding variables will be adjusted in the model. To explore whether THR effects are any different between participants recently discharged from the psychiatric hospital and those without recent psychiatric hospitalization, we will compare THR effects between these two groups of THR/BA participants by introducing three extra terms in the model for Aim 1. They include an indicator variable (RecentHosp) for this sub-classification (with or without recent hospitalization) and the intervention*RecentHosp and intervention*RecentHosp*time interaction terms. Contrasts will be set up to test the effect of interest and 95% CI for this effect assessment will be calculated

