on 18 THR and 11 BA, participants with concomitant psychiatric diagnosis and six-months follow-up ABC-C data from our RCT, the ES for THR effect on the six-month irritability score was 0.45 (not published) as compared to BA participants. In this case, we will have 81% power for the primary ITT analysis (n=81 per arm) to detect the THR effect on ABC-C, but 56% power to see statistical significance for completer analysis. This analysis assumes that 45 participants per arm will be followed six-months after the intervention. Aim 3 is more hypothesis generating and exploratory. 20 extra participants will be enrolled in the wait list group who subsequently received Hybrid intervention. To minimize the imbalance between groups, we will randomize with 1:1:1 ratio the first 60 Colorado participants into BA/THR/wait list group. The minimum detectable effect size needs to be 0.9 (0.74) Cohen's D to have 80% power if 20 wait list (or Hybrid) participants

will be compared to 20 (or 56) other participants.

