Aim 2 determines if THR outcomes are maintained over time. We propose to address the paucity of HAI research examining long-term maintenance of effects. In addition to our six-month follow-up report¹⁸ in a subset of participants in our THR RCT¹³, to our knowledge, only one other study to date has attempted to prospectively examine residual effects of THR in children with ASD, but it had several methodological limitations including teacher-report measures, lack of a control condition, and an unplanned six-week break during the initial treatment phase.⁹⁶ Information on longer term THR effects has important clinical practice implications, including the possibility that THR could be an adjunctive intervention to the current practice of using psychotropic medications to reduce symptoms of aberrant behaviors in ASD youth.⁷⁴

Aim 3 explores dose and sub-population effects of THR and Barn Activity (BA) interventions. This aim addresses important next steps to advance the HAI field of research. A recent systematic review of HAI research with the ASD population discussed the field’s tendency to employ diverse research methods that lack replication and use of non-homogenous ASD samples, which limits the ability to determine who might benefit the most from HAI and under which conditions.⁷¹ Exploratory analyses of our RCT¹³ sample showed stronger positive outcomes in the subgroup of THR participants with co-occurring psychiatric disorders, which provides support to focus on this group who stands to benefit the most from THR. Additionally, the BA no-horse control group in our RCT¹³ showed significant within-group improvements in irritability and hyperactivity behaviors at the conclusion of the intervention, but we were unable to draw conclusions about the effects of that BA group due to the absence of a nonintervention control. Thus, we aim to both explore the effects of BA compared to a waitlist control and explore the dosing effects of a Hybrid group (i.e., 5 weeks BA followed by 5 weeks THR).

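### H3b claims that Hybrid responds like THR, but the only Hybrid–THR criterion is a test for a difference, which can contradict similarity and cannot support it

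*Protocol*

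**What the plan says.** Specific Aim 3 sets two hypotheses of different kinds. H3a is a superiority claim, BA over waitlist. H3b is a similarity claim: "The Hybrid group will show a similar response pattern as the THR group". The Hybrid programme is five weeks of BA followed by five of THR, and the section Summarize Knowledge to be Gained presents the comparison as a way to "explore the dosing effects of a Hybrid group".

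The Exploratory AIM 3 text plans two Hybrid comparisons: the Hybrid period against the same child's wait period, and then "Moreover, we will compare hybrid treatment participants to all BA and THR participants". One rule covers both H3a and H3b: "the between-group difference in outcome change between baseline and 10 weeks will be used to assess efficacy and tested for statistical significance". The significance level is set under General consideration of statistical analysis: "In all analyses, a $p \leq 0.05$ will be considered significant". A 95% confidence interval and Cohen's d are also to be reported. No margin or other definition of a similar response is given.

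The Power analysis states for Aim 3 "The minimum detectable effect size needs to be 0.9 (0.74", that is, 0.9 for 20 children against 20 others and 0.74 against 56, at 80% power. It describes Aim 3 as exploratory and hypothesis generating. Specific Aim 3 and the Power analysis put the Hybrid group at 20, but the Randomization section says "After at least 24 participants have completed the waitlist/hybrid arm, this assignment will discontinue".

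**The concern.** A test of no difference suits H3a, where a significant result supports the hypothesis. For H3b it points the wrong way: a significant Hybrid–THR difference contradicts the hypothesis, while a non-significant one may mean that the groups are alike or only that the sample is small. No outcome of the stated test counts in favour of H3b.

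The matter at stake is the dose question. If five weeks of THR after five of BA is to be described as matching ten weeks, the evidence must be able to tell a short course that works fully from one that has lost much of the benefit. With 20 to 24 Hybrid children a difference test separates these poorly, and the protocol offers nothing else by which similarity to THR would be judged.

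**Working it through.** **Inputs.** Hybrid n = 20 (Specific Aim 3, Power analysis) or 24 (Randomization). THR n = 56 (completers), 71 (enrolled per arm) or 81 (Table 2, ITT), all from the Power analysis. Whole THR–BA effect on irritability d = 0.62 (Power analysis). Level 5%; two-sided is my assumption and it reproduces the stated figures. THR–BA is the natural yardstick because Hybrid contains five weeks of BA: a Hybrid group no better than BA would differ from THR by 0.62, and one that kept half the benefit by 0.31.

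**Formulas, in SD units.** SE = √(1/n₁ + 1/n₂). Power comes from the noncentral t distribution with n₁ + n₂ − 2 degrees of freedom and noncentrality d/SE. The detectable effect is the d that gives 80% power. The 95% CI half-width is t₀.₉₇₅ × SE.

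**Reproducing the plan.**
- 20 v 20: SE = 0.316, detectable d = 0.909 (stated 0.9).
- 20 v 56: SE = √(0.0500 + 0.0179) = 0.2605, detectable d = 0.739 (stated 0.74).
- d = 0.62 gives 90.2% power at 56 per arm and 97.5% at 81 per arm (stated 90% and 97%).

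**Hybrid v THR for the sizes the protocol allows.**

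| Hybrid v THR | SE | Detectable d, 80% power | P(non-significant), true difference 0.62 | P(non-significant), true difference 0.31 | 95% CI half-width |
|---|---|---|---|---|---|
| 20 v 56 | 0.260 | 0.74 | 35% | 78% | 0.52 |
| 20 v 71 | 0.253 | 0.72 | 32% | 77% | 0.50 |
| 20 v 81 | 0.250 | 0.71 | 31% | 77% | 0.50 |
| 24 v 56 | 0.244 | 0.69 | 29% | 76% | 0.49 |
| 24 v 71 | 0.236 | 0.67 | 26% | 75% | 0.47 |
| 24 v 81 | 0.232 | 0.66 | 25% | 74% | 0.46 |

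For the first row: noncentrality 0.62/0.2605 = 2.38, critical t = 1.99, power 65%, so 35% non-significant; half-width 1.99 × 0.2605 = 0.52.

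**Reading the interval.** With an observed Hybrid–THR difference of exactly zero, the interval would reach 0.46 to 0.52 SD. That is 0.46/0.62 = 74% to 0.52/0.62 = 84% of the THR–BA effect, so loss of half the benefit could not be excluded.

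**Sensitivity to the effect size.** The Power analysis prints changes of 6.9 (SEM 1.66, n = 27) and 2.3 (SEM 1.8, n = 26). If these are raw standard errors, the SDs are 1.66√27 = 8.63 and 1.8√26 = 9.18, pooled 8.9, and d = 4.6/8.9 = 0.52. A Hybrid group no better than BA would then give a non-significant test in 40% (24 v 81) to 50% (20 v 56) of trials.

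**What a margin would demand.** Take half the effect, 0.31 SD, purely as an example. With a true difference of zero, one-sided 2.5% non-inferiority needs 164 per arm for 80% power. The planned 20 v 56 gives about 22%.

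**The case against.** The strongest reply is that the harm is not written down. A reader might infer that a non-significant Hybrid–THR test will be declared similarity. No section says so, and the percentages above are rates of non-significance, not rates of a planned declaration. That stands, and the point must not be put more strongly.

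Other parts of the reply also stand. Aim 3 is labelled exploratory, its wording speaks of comparing effect sizes, and the detectable effects are printed openly. A 95% CI with Cohen's d is planned. The wait-period and Hybrid–BA comparisons bear on whether Hybrid works, so the dose question does not rest on one test. They do not show that Hybrid matches THR, however. Hybrid–BA is no more precise: if Hybrid were fully as good as THR, its 0.62 advantage over BA would be missed at the same 25–35% rate for the same group sizes.

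Two stronger readings should be set aside. One is that only differences larger than the whole THR effect can be detected. That holds at 80% power only: with 20 v 56 an observed difference of about 0.52 SD is significant, and a true 0.62 is found 65% of the time. The other uses the 20 v 20 figures (52% and 84% non-significant). The concurrently randomised set is described for H3a; for H3b the analysis text names all BA and THR participants.

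It can also be said that a criterion for similarity belongs in the SAP, which is not at hand. But the protocol does more than stay silent: it assigns to H3b a test that cannot support it.

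**Conclusion.** The mismatch between hypothesis and test is real and follows from the protocol's own text. Its practical size is that the detectable Hybrid–THR difference at 80% power, 0.66 to 0.74 SD, exceeds the whole planned THR–BA effect of 0.62. A Hybrid group with no advantage over BA would fail to differ significantly from THR about 25–35% of the time, and one that kept half the benefit about 74–78%. These figures assume a two-sided 5% t-test as a stand-in for the mixed model, d = 0.62 as the full effect, 20 or 24 Hybrid children and 56 to 81 THR children.

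Because Aim 3 is exploratory, an interval is already planned, and no rule equates non-significance with similarity, this is a minor-to-moderate point about what may be concluded on dose. It does not touch Aims 1 and 2.

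**What to change.** In the Exploratory AIM 3 text, state that a non-significant Hybrid–THR test is not evidence for H3b. Then choose one of two routes.

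- Restate H3b as estimation: report the Hybrid–THR difference with its 95% CI and read it together with the Hybrid–BA estimate that is already planned.
- Keep H3b as a similarity claim and judge the planned CI against a margin that the investigators fix in advance as a fraction of the THR–BA effect. Half of it, 0.31 SD, is only an illustration; the choice is theirs.

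The first route fits the sample better, since the interval half-width of 0.46 to 0.52 SD already exceeds 0.31. Reconcile the Hybrid group size (20 or at least 24) in the same edit.

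The cost is two or three sentences, with no new data and no change to conduct. The downside is that with 20 to 24 Hybrid children H3b will probably be reported as unresolved.

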
The objective of this proposed RCT is to identify physiological mediators of our well-tested^{13,15} 10-week manualized¹⁶ THR intervention compared to a similarly structured BA control group in up to 250 youth ages 6-16 yrs. with ASD and co-occurring psychiatric disorders recruited from the community, outpatient clinics, and a psychiatric hospital setting. An additional 20 ASD youth with co-occurring psychiatric disorders will be recruited for the exploratory aim's waitlist control and Hybrid intervention groups.

Specific Aim 1: Examine physiological mediators in a THR intervention group compared to a BA control on multivariate outcomes by measuring individual physiological response profiles and analyzing them for predictive validity and mediating effects on primary (irritability, hyperactivity), secondary (social communication, social cognition, and word fluency) and expanded outcomes (emotional dysregulation, caregiver QOL, and crisis mental health care usage).

Hypothesis 1a (H1a). *THR group will have significantly greater improvement in outcomes collected at baseline compared to post-intervention. H1b: Post-intervention (week 10) afternoon salivary cortisol levels will be significantly reduced (indicating less stress) in the THR group compared to baseline/week one levels. H1c. THR group will have a decrease in heart rate and electrodermal activity and an increase in heart rate variability, both indicating a calm state, from baseline to post- intervention. H1d. Physiological measures collected at intervention midpoint and post-intervention) will be correlated with and largely explain/mediate the effects of THR on post-intervention outcomes.*

Specific Aim 2: Evaluate the durability of Aim 1 outcomes in the THR group compared to the BA group control six-months post intervention period. *H2. THR group will maintain significantly greater outcome gains six-months after the intervention compared to the BA control.*

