Salivary Cortisol: Cortisol can be measured accurately in a minimally invasive manner via saliva, and the hypothalamic Pituitary Adrenal (HPA) axis is fast acting in response to environmental conditions. Typically, HPA activity shows a distinct non-linear circadian rhythm. In TD individuals, cortisol levels increase before awakening, show a rapid rise from awakening to +30-45 min, and a daily fall, with levels lowest during the normal sleep cycle before repeating.¹¹⁹ Circadian cortisol rhythms in children with ASD are not always consistent with matched TD controls, instead displaying lower AM and higher PM levels.¹²⁰ However, preliminary evidence suggests that afternoon salivary cortisol levels in ASD youth are less irregular, indicating that afternoon sampling may be a more reliable measure of stress for this population.¹²¹ Each participant will donate approximately 0.5-1 mL of saliva at the riding center immediately before and 20 minutes after each THR or BA group session weeks 1-10. Salivary cortisol collections will only be analyzed for weeks 1, week 5 or the adjacent week if participant misses session 5, and week 10. Collection methods will be the same as previously reported in our replication pilot.¹²² In brief, THR and BA interventions will occur in the afternoons (between 1:00-5:00 PM) to avoid the sharp rise and fall in cortisol levels in the AM associated with diurnal patterns of HPA axis activity. Only saliva samples taken at weeks 1, 5, and 10 of the intervention will be assayed for cortisol. Saliva samples will be collected using absorbent swabs designed for use with youth (Salivabio, LLC, Carlsbad, CA). They will be temporarily stored frozen at the riding centers, then transported to the respective hospital research site for storage in a freezer until shipped to Salimetrics for analysis. Caregivers will receive the following instructions prior to collection days: (1) Participants should avoid eating a substantial meal (other than a snack) and drinking liquids other than water within 30 minutes prior to collection time and (2) cannot brush their teeth for at least 45 minutes prior to collection time. Participants who do eat within the hour before collection will be asked to drink water and then wait 10 minutes before collections.¹¹¹

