Adequacy of Protection Against Risks: The risks to participants regarding THR are mitigated by this study's use of two sites that are PATH Intl.¹⁷ Premiere Accredited Centers. Première accreditation status means they follow rigorous standards and comply with site visits every five years to assess the sites' infrastructure as well as ensure safe and effective operations for horses and humans throughout all areas of programming. *More information about these center accreditation standards can be accessed by visiting the PATH Intl. website at www.pathintl.org.* The standard procedures used by the therapeutic riding centers for this proposal decreases risks to the riders and staff implementing safety policies standard in the field and according to PATH Intl. guidelines. Such safety standards include the following: requiring participants wear protective gear, monitoring the temperament of the horses, training horses to participate in therapeutic horseback riding experience with children who have a variety of disabilities, and instructing participants about safe practices around horses. In addition, PATH Intl. certified instructors will be conducting the therapy. These instructors have demonstrated PATH Intl. competency in the areas of equine management, horsemanship, riding instruction, teaching methodology and knowledge of disabilities. These instructors also have Cardiopulmonary resuscitation (CPR) and First Aid certifications. (See riding centers' participant rider safety standards and procedures information in the Appendix documents.)

Participant Discontinuation Criteria: Participants who miss more than two out of the 10 THR, BA or Hybrid intervention lessons will automatically be dropped from the study. Participants who develop significant allergic reactions to conditions at either of the riding centers (CO or ME) will, at the discretion of the caregiver or the riding center staff, be dropped from the study. There are no protocol-stopping criteria as there are no *a priori* hidden risk concerns from which to build criteria. The participant discontinuation criteria will adequately protect study participants.

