Data auditing and cleaning: HRV: Following the authoritative guidelines given in the Task Force,¹³³ data will be band-passed filtered (0.5-45Hz), heartbeats will be detected by automatic multiscale-based peak detection,¹³⁴ and lost data and/or premature atrial/ventricular contractions corrected via cubic spline interpolation. Time-domain indices (HR; SD; root-mean square of successive differences, RMSSD) will be calculated per standard methods. Frequency-domain indices (LF, low-frequency power; HF, high-frequency power) will be calculated via Lomb-Scargle Periodogram, and reported as natural log values. Standard covariates will be applied, and data quality reporting indices will be reported.^{135,136} EDA will be decomposed into tonic and phasic activity using standard methods⁴⁰ and de-noised depending on the accelerometer data – periods of high physical activity will be removed from the analysis period. The mean, SD, and non-specific skin conductance responses (NSSCRs; bursts of activity over 0.2uS) will be extracted per time period. NSSCRs will be reported as depolarizations per minute. Signal quality for both physiological records, which is frequently problematic during ambulatory recording, will be maintained through the combined use of automated tools for quality control,¹³² visual artifact identification, and redaction.¹³⁷

During each 10-week intervention (THR and BA), [name] lab team will meet with study PI, [name] and RAs from Colorado and Maine sites to monitor the Shimmer ECG (HR/HRV) and EDA data collected for quality and for possible equipment failure issues. [name] lab team in collaboration with [name] will then determine which data points collected will be used for analyses, ensuring that each subject has a beginning point (Lesson 1 or alternate lesson 2 or 3), midpoint (Lesson 6 or alternate lesson 7), and endpoint = (Lesson 10 or alternate lesson 9 or 8).

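### Cortisol has no substitute sample when lesson 1 or lesson 10 is missed, although saliva is frozen every week and alternates at both ends are allowed for ECG and EDA

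*Protocol*

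**What the plan says.** **Collection and storage.** Under Salivary Cortisol, saliva is taken "immediately before and 20 minutes after each THR or BA group session weeks 1-10". Of the samples it says: "They will be temporarily stored frozen at the riding centers, then transported to the respective hospital research site for storage in a freezer".

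**Which samples are used.** The same paragraph gives two rules. The first is "Salivary cortisol collections will only be analyzed for weeks 1, week 5 or the adjacent week if participant misses session 5, and week 10". The second, a few sentences later, is "Only saliva samples taken at weeks 1, 5, and 10 of the intervention will be assayed for cortisol".

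**Permitted absence.** The Participant Discontinuation Criteria state: "Participants who miss more than two out of the 10 THR, BA or Hybrid intervention lessons will automatically be dropped from the study". A child may therefore miss two lessons and remain in the study.

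**The sensor measures.** Data auditing and cleaning describes meetings "to monitor the Shimmer ECG (HR/HRV) and EDA data collected for quality and for possible equipment failure issues". It then sets a start point (lesson 1, else 2 or 3), a midpoint (lesson 6, else 7) and an "endpoint = (Lesson 10 or alternate lesson 9 or 8". Cortisol is not named there. The EDA and HR/HRV paragraphs under Study Measures give those signals the same rule as the first cortisol sentence: week 1, week 5 or an adjacent week, and week 10.

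**The hypotheses.** H1b reads: "Post-intervention (week 10) afternoon salivary cortisol levels will be significantly reduced (indicating less stress) in the THR group compared to baseline/week one levels". H1d names physiological measures at the midpoint and after the intervention as mediators.

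**The concern.** The protocol foresees missed lessons and, in one section, provides for them at both ends of the course for ECG and EDA. For cortisol it fixes a rule that leaves a neighbouring stored sample unassayed when lesson 1 or 10 is missed. Read literally, the second cortisol sentence also cancels the session-5 substitute that the first allows.

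At stake is avoidable loss of cortisol values. H1b rests on the change from week 1 to week 10. The mediation analysis includes only participants with both mediator and outcome, and it defines the mediator as a change from baseline. Cortisol is also the mediator that the Specific Aims single out as a viable target.

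**Working it through.** **1. Who is affected, by analysis.**
- *H1b.* The AIM1 efficacy paragraph assigns H1a to H1c to a linear mixed model. The general considerations section analyses all randomized participants and makes that model the primary method for missing values. A child with one of the two cortisol values stays in the model but supplies no within-child change.
- *H1d, midpoint mediator.* The change needs week 1 and the midpoint. A missing week 1 removes the child; a missing week 10 does not.
- *H1d, week-10 mediator.* The change needs weeks 1 and 10. Either one missing removes the child.

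**2. How often absence costs a sample.** Assumption: all patterns of k missed lessons out of 10 are equally likely.

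| | k = 1 (10 patterns) | k = 2 (45 patterns) |
|---|---|---|
| Week 10 missing | 1/10 = 10% | 9/45 = 20% |
| Week 10 missing, lesson 9 attended | 1/10 = 10% | 8/45 = 17.8% |
| Week 1 or week 10 missing | 2/10 = 20% | 17/45 = 37.8% |
| Start or end missing if the ECG/EDA alternates applied | 0/10 | 0/45 |

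The third row is 1 − C(8,k)/C(10,k). The last row is zero because emptying either window (lessons 1 to 3 or 8 to 10) takes three absences.

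**3. Mediation power.** Inputs from Power analysis: a = 0.4, b = 0.43, total effect c = 0.34, n = 2 × 56 = 112, two-sided 5%. With the indirect path explaining half the total effect, the direct effect is c′ = 0.34 − 0.17 = 0.17. In standardized form:
- var(a) = (1 − a²)/n = 0.84/112 = 0.00750
- residual variance of the outcome = 1 − (b² + c′² + 2abc′) = 1 − (0.1849 + 0.0289 + 0.0585) = 0.7277
- var(b) = 0.7277/(112 × 0.84) = 0.00774
- z = ab/√(a²·var(b) + b²·var(a)) = 0.172/√(0.00124 + 0.00139) = 3.36
- power = Φ(3.36 − 1.96) = 92%, close to the plan's 90%.

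z scales with √n. If every child missed exactly one lesson:
- midpoint mediator (week 1 missing in 10%): 112 × 0.90 ≈ 101, power 89%. This assumes that a missed midpoint is replaced by the adjacent week;
- week-10 mediator (either end missing in 20%): 112 × 0.80 ≈ 90, power 85%.

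**4. H1b.** The protocol gives no cortisol effect size, so only a range can be shown. Take 56 children in the THR arm, a paired t test on complete pairs, and assumed standardized changes of 0.3, 0.4 and 0.5. Power is 60%, 84% and 96% with all 56. It is 55%, 79% and 93% with 50 (10% loss), and 49%, 74% and 90% with 44 (20% loss). Because the planned mixed model keeps children with one value, complete pairs may overstate the loss.

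**The case against.** A reader might infer that children who miss lesson 10 are lost from H1b. The documents do not support that: the mixed model retains them, and restriction to available data is stated only for mediation. A reader might also infer that the values are discarded for no reason. The protocol gives no reason, but H1b names week 10 and week one, and a fixed time point is a legitimate choice. A sample taken after one or two attended lessons would not be a clean baseline. That objection does not touch a pre-lesson sample at the first lesson attended, nor lesson 9 standing in for lesson 10.

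The contrast with ECG and EDA is less clean than it looks. The EDA and HR/HRV paragraphs state the same weeks as cortisol, so the data-cleaning section conflicts with them too, and its alternates arise in a review of signal quality and equipment failure. This stands, and it is a further reason to reconcile all four places. Nor can the rule be blamed for cortisol and sensor data covering different children: the feasibility pilot leads the authors to expect only about 85% sensor data retention in any case.

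On size, no absence rate is given, and every child missing one lesson is only a scenario. The population section allows up to 250 participants, against the 142 behind the 112, so actual power could be higher.

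Finally, substitution rules are often left to the analysis plan. Here, however, the protocol states a definite rule, in two versions that disagree.

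**Conclusion.** The point holds as a stated rule that gives up usable data and contradicts itself. Applied literally, it leaves children who miss lesson 1 or 10 without a cortisol change value while a neighbouring sample stays frozen. A missing week 1 removes a child from every cortisol mediation analysis; a missing week 10 removes the child only from the post-intervention version. In neither case is the child excluded from the H1b model.

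Under random absence, the share with week 1 or week 10 missing is 20% after one missed lesson and 37.8% after two. The power figures of 89% and 85% belong to mediation and rest on the plan's assumed paths and an absence scenario that the documents do not support or rule out. The effect is moderate, but avoidable at little cost.

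**What to change.** Before samples are selected for assay, state one cortisol rule consistent with the data-cleaning section:
- **Start:** the pre-lesson sample of the first lesson attended. With at most two absences this is lesson 1, 2 or 3, and it precedes any exposure.
- **Midpoint:** the adjacent lesson if the nominal one is missed.
- **End:** the last attended of lessons 10, 9 or 8.

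Delete the sentence restricting assays to weeks 1, 5 and 10. Reconcile the cortisol, EDA and HR/HRV paragraphs with the data-cleaning section, including whether the nominal midpoint is 5 or 6. State which sample is the start for children who postpone after one or two lessons, since they do not repeat those lessons. Add a sensitivity analysis using exact week-1 and week-10 samples only.

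The cost is a short text change, with no extra collection and no more assays per child than planned. It works for any sample still in storage. The downside is an endpoint one or two weeks early for some children, which the data-cleaning section already accepts for ECG and EDA.
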